7. IMPLEMENTATION

7.1. Examination parameters before study start

1. Medical history, e.g. histological findings, HR status findings, WHO status (within one month prior to randomisation)
2. Clinical examinations (within one month prior to randomisation):
 - Clinical examination
 - Gynaecological examination
3. Radiological investigations (within one year prior to randomisation):
 - Sonography of the abdomen or abdominal CT
 - Chest x-ray or CT
 - Bilateral mammogram (unilateral mammogram in the case of mastectomy)
 - Bone density measurement (optional)
4. Laboratory parameters (within 3 months prior to randomisation):
 - LFP (GOT, GPT, total bilirubin, AP)
 - RFP (serum creatinine)
 - Optional tumour markers: CEA, CA 15-3

7.2. Examination parameters during the study

7.2.1. After 6 months (Arm A and B)

1. Clinical examination
2. Survey of fracture rate
3. Adverse events leading to discontinuation of therapy
4. Severe adverse events

The time frame for these examinations is defined as +/- 6 weeks.

7.2.2. After 12 and 24 months (Arm A and B)

1. Clinical examination
2. Survey of fracture rate
3. Adverse events leading to discontinuation of therapy
4. Serious adverse events
5. Laboratory parameters:
 - LFP (GOT, GPT, total bilirubin, AP)
 - RFP (serum creatinine)
 - Optional TU marker: CEA, CA 15-3
6. Gynaecological examination
7. Radiological examinations
 - Sonography of the abdomen or abdominal CT
 - Chest x-ray or CT
 - Bilateral mammogram (unilateral mammogram in the case of mastectomy)
 - Bone density measurement (optional)

The time frame for these examinations is defined as +/- 6 months. If the patient does not attend the visit at the designated interval, this results in the patient being set to the off position.

7.2.3. After 36, 48 and 60 months (Arm B)

1. Clinical examination
2. Survey of fracture rate
3. Adverse events leading to discontinuation of therapy
4. Serious adverse events
5. Laboratory parameters:
 - LFP (GOT, GPT, total bilirubin, AP)
 - RFP (serum creatinine)
 - Optional TU marker: CEA, CA 15-3
6. Gynaecological examination
7. Radiological examinations
 - Sonography of the abdomen or abdominal CT
 - Chest x-ray or CT
 - Bilateral mammogram (unilateral mammogram in the case of mastectomy)
 - Bone density measurement (optional)

The time frame for these examinations is defined as +/- 6 months. If the patient does not attend the visit at the designated interval, this results in the patient being set to the off position.

7.3. Follow-up

After the therapy is complete, follow-up examinations are carried out at yearly intervals (+/- 6 months) for a period of 8 years in Arm A and 5 years in Arm B.

1. Clinical examinations
2. Bilateral mammogram (unilateral mammogram in the case of mastectomy)
3. Serious adverse events (see 9.1 and 9.2.4)

Written contact with the patient to obtain findings is permitted. It is also possible to check the patient's status (living or deceased) via the Central Registration Office (ZMA) or the GP. If the patient does not attend a visit for more than 2 years during the follow-up period, this results in the patient being set to the off position.

8. METHODS

8.1. Methods/parameters relating to efficacy

DFS:	Time from randomisation to onset of any of the following events: 
 • Occurrence of a relapse (locoregional relapse, distant metastasis) • Occurrence of a secondary cancer (except basal cell carcinoma of the skin, in-situ carcinoma of the cervix or LCIS) • All deaths regardless of cause
Overall survival:	Time from randomisation to onset of death, regardless of the cause
Locoregional relapse:	
Definition: 1. Relapse in the operated breast 2. Chest wall relapse on the operated side 3. Axillary lymph node recurrence
 
In addition to the exact date of verification of the locoregional recurrence, the type of diagnostic measure used is documented in detail.

Distant metastasis:	
Definition: 1. All distant lymph node metastasis (supraclavicular, internal mammary lymph nodes, contralateral axilla) 2. All organ metastasis
 
In addition to the exact date of the verification of the metastasis, the type of diagnostic measure used is documented in detail.

Event:	
Definition: 1. Locoregional recurrence 2. Contralateral breast cancer 3. Distant metastasis 4. Fatality regardless of the cause

Fracture rate:	
The occurrence of fractures is assessed according to the following locations:
 
 • Hip • Lumbar spine • Radius • Other

8.2. Concomitant diseases

Concomitant diseases that do not fall under the exclusion criteria referred to in 5.3., such as diabetes mellitus, hypertension etc., should be stabilised with suitable medication before inclusion in the clinical trial.

8.3. Concomitant therapy

With the exception of anastrozole, no other systemic breast cancer treatments may be used for the entire duration of the study.

The administration of substances that have an influence on the status of sex hormones (e.g. prednisolone, hormone replacement with oestrogen or progesterone) is not permitted with the exception of topical application of oestrogen and use of phytoestrogens.

For all other medications, there are no restrictions.

According to the guidelines from the American Society of Clinical Oncology [37] (Appendix B), postmenopausal women receiving aromatase inhibitors as part of their adjuvant therapy are always classified as “high risk” for developing therapy-induced osteoporosis.

For these patients, and thus for all patients within this study, the following recommendations apply:

- Ongoing monitoring of bone density (once a year)
- If T score >-1 : Observance, life style recommendations, possibly calcium + vitamin D
- If T score >-2.5 and <-1 : Life style recommendations, calcium + vitamin D
- If T score >-2.5 : Life style recommendations, calcium + vitamin D **and** Therapy with bisphosphonates

With the exception of osteoporosis-associated therapy, concomitant medications do not need to be documented in the CRF.

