1.2. Flow chart

Parameter	Screening	6 months	12 months	24 months	36 months	48 months	60 months	6 years	7 years	8 years	9 years	10 years
Verification of inclusion and exclusion criteria	X											
Medical history	X											
Clinical examination	X	X	X	X	X	X	X	X	X	X	X	X
Gynaecological examination	X		X	X	X	X	X					
Ultrasound or CT of abdomen	X		X	X	X	X	X					
Chest x-ray or CT	X		X	X	X	X	X					
Bilateral or unilateral mammogram	X		X	X	X	X	X	X	X	X	X	X
Measurement of bone density (optional)	X		X	X	X****	X****	X****					
Survey of fracture rate		X	X	X	X	X	X					
LFP*	X		X	X	X	X	X					
RFP**	X		X	X	X	X	X					
TU marker*** (optional)	X		X	X	X	X	X					
SAE/AE												
				See point 9							See point 9	

Legend: * LFP: GOT,GPT, AP, total bilirubin

** RFP: Serum creatinine

*** TU marker: CEA, CA 15-3

**** Only for patients in Arm B (5 years of anastrozole)

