7.2.2. After 12, 24, 36, 48 and 60 months

1. Physical examination
2. Survey of fracture rate
3. Adverse events leading to discontinuation of therapy
4. Serious adverse events
5. Development of hepatic, renal insufficiency
6. Optional TU marker: CEA, CA 15-3
7. Gynaecological examination
8. Radiological examinations
 - Sonography of the abdomen or abdominal CT
 - Chest x-ray or CT
 - Bilateral mammogram (unilateral mammogram in the case of mastectomy)
9. Bone density measurement (optional)

Affected protocol point:

- 7. Implementation
- 7.3. Follow-up (page 28)

Old text:

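### Protocol 8.3 prints the bisphosphonate threshold as T > -2.5, which covers both milder bands and leaves T ≤ -2.5 with no treatment line

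*Protocol*

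**What the plan says.** Protocol section 8.3 (Concomitant therapy) cites a 2003 oncology-society guideline, reproduced as Appendix B. It classes postmenopausal women on adjuvant aromatase inhibitors as at high risk of therapy-induced osteoporosis and applies its recommendations to every patient in the study. One bullet recommends yearly bone density monitoring and is not tied to a T score. The other three are:

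- Bullet 1: "If T score >-1 : Observance, life style recommendations, possibly calcium + vitamin D".
- Bullet 2: "If T score >-2.5 and <-1", with lifestyle advice, calcium and vitamin D.
- Bullet 3: "If T score >-2.5 : Life style recommendations, calcium + vitamin D". The bullet then adds bisphosphonate therapy.

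On other drugs the section says "For all other medications, there are no restrictions". On recording it says "With the exception of osteoporosis-associated therapy, concomitant medications do not need to be documented in the CRF".

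The flow chart (1.2) and the visit lists (7.1 and 7.2, and their Amendment 1 versions) mark bone density measurement as optional. None of Amendments 1 to 3 as supplied lists section 8.3 among the points it changes, and the SAP contains no T-score rule.

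**The concern.** Treatment escalates from bullet 1 to bullet 3, so the bisphosphonate line should belong to the lowest bone densities. As printed it belongs to every T score above -2.5. That includes women whose bone density bullet 1 treats as needing little more than observation. The lowest T scores have no treatment line at all.

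This is an operative treatment threshold, not background text. Followed literally, it would direct bisphosphonate advice to the wrong patients. The trial drug makes this relevant: Table 2 in Protocol 2.3.2 reports fractures in 5.8% of patients on anastrozole against 3.7% on tamoxifen. Fracture is also a secondary endpoint. SAP 3.6.4 counts time to first clinical fracture from two years after randomisation and censors at the last therapy visit, at most about five years after randomisation. That is the window in which planned anastrozole exposure differs between the arms.

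**Working it through.** No formula or distributional assumption is needed; the check is whether each T score falls in exactly one of the three bands. The inputs are the three intervals in Protocol 8.3: bullet 1, T > -1; bullet 2, -2.5 < T < -1; bullet 3, T > -2.5.

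**Bullets that apply at selected values**

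| T score | As printed | Bullet 3 as T ≤ -2.5 | Bullet 1 also as T ≥ -1 |
|---|---|---|---|
| 0 | 1 and 3 | 1 | 1 |
| -1 | 3 | none | 1 |
| -2 | 2 and 3 | 2 | 2 |
| -2.5 | none | 3 | 3 |
| -3 | none | 3 | 3 |

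**Number of treatment lines by region**

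| Version | T ≤ -2.5 | -2.5 < T < -1 | T = -1 | T > -1 |
|---|---|---|---|---|
| As printed | 0 | 2 | 1 | 2 |
| Bullet 3 as T ≤ -2.5 | 1 | 1 | 0 | 1 |
| Bullet 1 also as T ≥ -1 | 1 | 1 | 1 | 1 |

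1. As printed, bullet 3 wholly contains bullets 1 and 2. A woman with T = 0 is told both that calcium and vitamin D are possible and that she should have them with a bisphosphonate.
2. Reversing the sign in bullet 3 removes every overlap. The equality must be included: with T < -2.5, a value of exactly -2.5 would still fall in no band.
3. One gap then remains, at exactly T = -1, because bullets 1 and 2 both use strict inequalities there. Writing bullet 1 as T ≥ -1 closes it.

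**Was there a scheduled difference between arms in bone density measurement?** The original flow chart limits measurement at months 36 to 60 to Arm B. Amendment 1, dated 21 March 2005, lists those visits without an arm limit in 7.2.2, and its 7.3 aligns Arm A with Arm B at months 36, 48 and 60. With a planned start of December 2003, the earliest month-36 visit is December 2003 + 36 months = December 2006, or June 2006 after subtracting the 6-month visit window. Both dates fall after the amendment, so no scheduled arm difference follows.

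No patient-level size can be computed. The documents give no T-score distribution, bone density measurement rate or bisphosphonate use.

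**The case against.** The strongest reply is that this is one character in a machine-read text that appears to be a translation and has other small slips. Stratum 3 in Protocol 10.2 has a stray plus sign that SAP 2.3 does not, and Protocol 2.2.1 prints a relative risk as a percentage. The guideline that 8.3 relies on is in Appendix B, of which only the title, source and abbreviations are readable here, and it may hold the correct cut-offs. The bullets are recommendations and contradict each other so plainly that a physician would notice. The intent is clear, because bullet 2 stops at -2.5, and nothing prevents a bisphosphonate at T ≤ -2.5. Both arms received the same advice, and no bias in any endpoint has been shown.

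Most of this stands, and it limits the point. An artefact cannot be fully excluded, although the less-than sign in bullet 2 came through correctly. The gap for T ≤ -2.5 is shown only for section 8.3, not for the unreadable appendix. Literal compliance is unlikely, and the bands act only where bone density is measured. What does not follow is that the text can stand: a reader has to override the printed threshold to use it safely.

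**Conclusion.** The point holds, as a minor one. Section 8.3 as printed attaches bisphosphonates to T > -2.5, overlaps both milder bands and gives T ≤ -2.5 no T-score-specific treatment line. It is best read as a reversed sign and not a deliberate choice, because a bisphosphonate line for all T > -2.5 would make the first two bullets pointless. The missing value T = -1 is a lesser boundary slip in the same list.

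The conclusion rests on the supplied text reproducing the protocol's signs correctly; confidence is medium for that reason. The consequence is a matter of patient care and clear instruction. Disease-free survival, sample size and analysis populations are untouched, and no effect on the fracture comparison is claimed beyond its being unquantified.

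**What to change.** Check bullet 3 against the source protocol and Appendix B. If they confirm the reading, change bullet 3 to T ≤ -2.5 and bullet 1 to T ≥ -1, so that each T score falls in exactly one band.

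Amendment 3 put the planned end of maximum treatment at June 2015 (SAP 2.1.1.1 prints December 2015). If treatment has ended, issue the correction as an erratum and state which cut-offs sites actually used.

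A useful but separate addition is a descriptive table, by arm, of the osteoporosis-associated therapy that 8.3 already requires in the CRF, presented alongside the fracture endpoint. SAP sections 3.4.3, 3.6.4, 3.7 and 3.8.2 name no such table.

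The cost is one document check, one sign, one boundary and, if adopted, one table from data already collected. Design, sample size and primary analysis do not change.

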9. ADVERSE EVENTS

Adverse events or serious adverse events are defined below. It is vitally important that all persons who are involved in the conduct of this clinical study are familiar with the content of this section of the Protocol. It is the job of each investigator involved in the study to ensure this happens.

9.1 Definition of “adverse event – (AE)”

An adverse event is the occurrence of a disorder or exacerbation of a pre-existing condition in the context of a clinical study and is independent of a possible causal relationship with the administration of the trial drug. Disorders may be subjective and objective symptoms of the disease, including laboratory abnormalities. Adverse events leading to discontinuation of therapy must be documented in both the medical history and in the CRF.

With the exception of AEs that lead to discontinuation of therapy and fractures, all other AEs that are non-serious are not documented in the CRF within this study. However, it is mandatory to record all adverse effects in the patient’s medical file.

9.2. Definition of “serious adverse event – SAE”

A serious adverse event is an event that:

- Has a fatal outcome (for whatever reason)
- Has led to an immediate threat to life
- Has necessitated an inpatient admission or has prolonged an inpatient stay
- Has led to a lasting or significant disability/incapacity for work
- Has caused congenital malformations
- Constitutes a malignant tumour

Other serious, medically relevant events that endanger the patient or require a medical intervention in order to protect them from the above-mentioned damage, are also classified as serious adverse events.

9.3. Reporting of serious adverse events by the investigator

9.3.1. Reporting during the therapy phase

If the AE is classified as serious by the investigator, an AstraZeneca-specific SAE Reporting Form must be filled out and sent to AstraZeneca by the investigator within 24 hours of discovery.

An original copy of the Reporting Form(s) and the fax confirmation(s) should be filed in the IF for the respective study site.

In addition, AstraZeneca undertakes to submit a quarterly statement of all SAEs that occurred in the context of the study to ABCSG Regulatory Affairs.

Details can be found in the study-specific SOPs under the item “Recording, assessment and reporting of serious adverse events”.

9.3.2. Reporting during follow-up or after discontinuation of therapy

The occurrence of serious adverse events in patients, in whom the study drug / study participation has been discontinued or terminated or the therapy has ended in line with the protocol only need to be reported if the adverse event occurred

- Within 30 days of discontinuing the study drug (drug incidents that are a causally linked to a follow-on therapy are not reported)
- More than 30 days after discontinuing the study drug, but the investigator cannot rule out a causal link with the previous therapy (anastrozole).

9.3.3. Reporting of protocol violations

Serious adverse events in patients who violate the protocol only need to be reported if the patient in question has already received the trial substance.

Irrespective of these exceptions, the investigator may at any time express to the sponsor that, in his opinion, an SAE should nevertheless be reported.

9.4. Reporting of serious adverse events by AstraZeneca

All SAEs reported to AstraZeneca are assessed, documented and evaluated according to the SOPs applicable to the clinical trial, and reported to the Federal Ministry for Women and Health and to AstraZeneca Drug Safety. Where applicable, SAEs are also reported to the hospitals in the Viennese Hospital Association [Wiener Krankenanstaltenverbund (KAV)].

In accordance with ICH-GCP, AstraZeneca will also inform all investigators involved of unexpected serious adverse effects of anastrozole occurring within the implementation of this clinical trial. This information will also be issued to the ABCSG.

9.5. Exceptions

The following events that occur over the course of Study 16 will not be reported as serious adverse events:

- Progression of the underlying disease or death as a result of the underlying disease
 - Hospitalisation:
 - Hospitalisation already scheduled or planned before enrolment in the study.
 - Hospitalisation to undergo purely diagnostic measures in particular, patient-related situations (such as elderly patients with a long journey to the study site). Hospitalisation would not normally be required.
 - Hospitalisation for cosmetic surgical measures.
- NB: Complications that occur during these hospitalisations are regarded as serious adverse events and are subject to the obligation to report!
- Accidents with demonstrable third party responsibility only (passive involvement of the patient).

However, all of these events must be documented in the medical records (traceable for the monitor) in each case until their conclusion.

10. STATISTICAL ANALYSIS

10.1. Sample size

From randomisation, all patients receive the same therapy for 2 years, and one group for a further 3 years. Any difference between the groups is thus only to be expected after 2 years from randomisation. Therefore, 2 years after randomisation (= change of therapy) is defined as the primary time of interest for the analysis for each patient.

It is expected that 700 patients may be recruited per year. Considering that 5% of the patients drop out in the first two years due to relapses, 665 patients per year remains an effective recruitment rate.

A difference between the treatment group and the control group of 0.916 and 0.937 after 3 years from the date of change of therapy in exponential survival (which corresponds to a hazard ratio of 1.35) can be disclosed with a power of 85% and a bilateral significance level of 5% when 433 events are observed. This will be achieved when 665 patients are recruited over 5 years and followed up for a further 2.7 years. This produces a sample size of 3500 patients of which 3325 are evaluable. The expected total duration of the study is 9.7 years. At an exponential drop-out rate of 7%, the power would reduce to 80%.

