12.6. Amendments

Changes to the final protocol should be made by means of amendments and are subject to approval by AstraZeneca. Amendments must be processed in accordance with the statutory provisions.

Protocol amendments that might affect the health interests of patients require a new vote from the Ethics Committee and an updated Informed consent/Patient information, insofar as they are affected by the changes. Administrative or technical changes to the protocol do not require a new vote from the Ethics Committee. The Ethics Committee will, however, be informed of all protocol amendments.

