## 2.4. Number of subjects - sample size estimation

As of randomization, all patients receive the same therapy for 2 years. After that, one group will continue the therapy for 3 further years. Therefore, differences between the groups are only to be expected 2 years after randomization. Therefore, the most relevant point in time regarding evaluation of the data will be 2 years after randomization (i.e. change of therapy) for each patient.

It is to be expected that 700 patients can be recruited per year. Considering that 5% of patients will drop out of the study within the first 2 years due to recurrence, an effective rate of recruitment of 665 remains.

A difference between the therapy group and the control group of 0.916 and 0.937 3 years after change of therapy at exponential survival (corresponding to a hazard quotient of 1.35) can be uncovered with 85% power at a two-sided level of significance of 5%, if 433 events are observed. This is feasible, if 665 patients are recruited annually for 5 years and followed up for another 2.7 years, amounting to a case number of 3,500, and of these 3325 evaluable patients. The expected total duration of the study is 9.7 years.

With an exponential drop-out rate of 7%, the power would be reduced to 80%.

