## 3.2. Types and time points of analyses

According to the protocol, the final analysis of the study should take place after a follow-up of 10 years for each patient. End of 2016 similar studies with prolonged endocrine therapy were presented to the scientific community. At this time, the required number of events was long since been reached. Therefore, the ABCSCG presidium decided in January 2017 to submit an abstract for the presentation at the San Antonio Breast Cancer Symposium (SABCS) in December 2017 based on an advanced analysis. The final analysis should take place approximately after 1 additional year. AstraZeneca agreed to these changes in April 2017.

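### The 433-event target does not match the 85% power or the accrual schedule stated with it; the error is conservative and minor

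*Protocol*

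**What the plan says.** Protocol 10.1 counts time from two years after randomisation, when the arms start to differ. It assumes exponential survival, 0.916 against 0.937 three years after that point, and gives the hazard ratio as 1.35. This difference "can be disclosed with a power of 85% and a bilateral significance level of 5% when 433 events are observed".

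The event number is then tied to a calendar: "This will be achieved when 665 patients are recruited over 5 years and followed up for a further 2.7 years". The accrual figure is net of a 5% loss to relapse in the first two years, since "665 patients per year remains an effective recruitment rate". On patient numbers, "This produces a sample size of 3500 patients of which 3325 are evaluable". Total duration is put at 9.7 years, which is 2 + 5 + 2.7.

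SAP 2.4 carries the same figures: the difference "can be uncovered with 85% power at a two-sided level of significance of 5%, if 433 events are observed", and "This is feasible, if 665 patients are recruited annually for 5 years and followed up for another 2.7 years". Neither document gives an allocation ratio or a sample-size formula.

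SAP 3.2 refers back to the target when it explains the change in analysis timing at the end of 2016: "At this time, the required number of events was long since been reached".

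**The concern.** Hazard ratio, significance level and power together fix the number of events. Hazards, patient number and calendar together fix how many events to expect. The plan states all of these quantities, so 433 can be tested in two independent ways, and it fails both.

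It is the only event target in either document, and SAP 3.2 leans on it. A reader who checks the sample size will find a target whose stated power is too low and whose stated schedule would not produce it. What is at stake is the accuracy of the power statement in the protocol, the SAP and any report that quotes them.

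**Working it through.** **Inputs** (Protocol 10.1, repeated in SAP 2.4): survival 0.916 and 0.937 at 3 years; exponential; two-sided 5%; power 85%; 433 events; 3325 evaluable patients; 5 years of accrual; 2.7 further years. Assumptions added here: 1:1 allocation, uniform accrual, no drop-out.

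**Step 1: hazard ratio.**
- λ₁ = −ln(0.916)/3 = 0.02925 per year
- λ₂ = −ln(0.937)/3 = 0.02169 per year
- Ratio 1.348, which rounds to the stated 1.35. This figure reproduces.

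**Step 2: events for 85% power.** z₀.₉₇₅ + z₀.₈₅ = 1.960 + 1.036 = 2.996; squared, 8.978.
- Schoenfeld, 4 × 8.978 / (ln HR)²: at 1.35, 35.91 / 0.0901 = 399; at 1.348, 35.91 / 0.0893 = 402.
- Freedman, 8.978 × [(HR + 1)/(HR − 1)]²: at 1.35, 405; at 1.348, 408.

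The stated 433 is not reproduced. It is 433/408 = 1.06 to 433/399 = 1.09 times the number needed.

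**Step 3: power at 433 events.**
- Schoenfeld, Φ(√433 × ln HR / 2 − 1.960): 87.5% at 1.348, 87.7% at 1.35.
- Freedman, Φ(√433 × (HR − 1)/(HR + 1) − 1.960): 87.0% at 1.348, 87.3% at 1.35.

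**Step 4: events on the stated schedule.** With accrual R = 5 and further follow-up F = 2.7, the probability of an event in an arm with hazard λ is

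1 − [exp(−λF) − exp(−λ(R + F))] / (λR).

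- Higher-hazard arm: 1 − (0.9241 − 0.7984)/0.1462 = 0.1403; × 3325/2 = 233.3 events.
- Lower-hazard arm: 1 − (0.9431 − 0.8462)/0.1085 = 0.1062; × 3325/2 = 176.6 events.
- Total 409.9, which is 23 fewer than 433.
- Power at 409.9 events: 85.2% to 85.9% over the two formulas and the two hazard ratios.

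This step does not depend on the power formula, and any drop-out would lower the count.

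**Step 5: does rounding or a variant explain 433?**
- Hazard ratios that round to 1.35 (1.345 to 1.355) need 389 to 415 events.
- Needing 433 events requires a hazard ratio of 1.334 (Schoenfeld) or 1.336 (Freedman), neither of which rounds to 1.35.
- A two-sided level of 0.049, allowing for 0.001 at the interim, needs 402 to 411. A one-sided 5% level needs 320 to 327.
- Unequal allocation would have to be about 37:63, which nothing in the documents suggests.

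**Step 6: when 433 events would be expected** (3325 patients, no drop-out).
- Original 5-year accrual: F = 3.01, so 2 + 5 + 3.01 = about 10.0 years in total.
- Recruitment from December 2003 to June 2010 (Amendment 3; SAP 2.1.1), that is 6.5 years: F = 2.28, so 2 + 6.5 + 2.28 = about 10.8 years.

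**The case against.** The best counter-argument is that this has almost no practical effect. A design with 87% power meets an 85% requirement. No planned analysis starts at the 433rd event or at 9.7 years: SAP 3.2 describes a final analysis after 10 years of follow-up, and 3.2.2 and 3.2.3 set cutoffs of 30 June 2016 and 30 June 2017. Patient number, significance level and test do not depend on the discrepancy. All of this stands, and it is why the point is minor.

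A second argument is rounding of the inputs. The survival rates are given to three decimals. Taken alone, 0.9165 against 0.9365 would be a ratio of 1.329, needing 444 to 450 events, so 433 lies within the range that rounding of the two rates allows. But the plan also states the ratio as 1.35, and no value that rounds to 1.35 needs 433. This narrows what can be said about rounding; it does not remove the discrepancy.

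A third is that 1:1 is assumed. That is true. It matters for Steps 2 and 3 and only slightly for Step 4. With two arms and minimisation, and no ratio mentioned, it is the natural reading.

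A reader might infer that the trial is underpowered, that the 3325 patients or the 2.7 years are wrong, or that SAP 3.2 is mistaken in saying the required number had long been reached. The documents support none of these. Waiting for 433 events gives more than 85% power, the stated schedule gives about 85% without it, and a target that is too high does not contradict a statement that it was passed. Nor does about 10.0 years describe the current plan: it belongs to the original 5-year accrual.

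**Conclusion.** The stated event number is wrong for the power and the schedule attached to it, in both documents. For 85% power about 399 to 408 events are needed; 433 events give about 87 to 88%; the stated schedule yields about 410 events and 85 to 86% power. The remaining figures (85%, 3325 patients, 5 + 2.7 years) are consistent with each other, so 433 is the one that does not fit, by 6 to 9% against the power and by 23 events against the schedule. The documents do not show where it came from.

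The error is conservative and the severity is minor. The result rests on 1:1 allocation, exponential survival with the stated rates, uniform accrual and no drop-out.

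**What to change.** Keep 433, so that the target is not revised after the events have accrued, and correct what is attached to it. In SAP 2.4, state:

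> 433 events give about 87% power under 1:1 allocation. The originally planned schedule (5 years of accrual plus 2.7 years, 3325 evaluable patients, no drop-out) is expected to yield about 410 events, about 85% power.

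If a date for 433 events is also given, either label it as belonging to the original 5-year accrual (about 10.0 years) or recompute it for recruitment to June 2010 (about 10.8 years, assuming uniform accrual over 6.5 years and no drop-out).

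For protocol 10.1, section 12.6 applies: "Changes to the final protocol should be made by means of amendments", with sponsor approval. Alternatively, the correction can be recorded in SAP section 4, which already lists departures from the protocol.

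The cost is a few sentences. Patient number, event target, significance level, test and follow-up do not change.
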